5.2.2 Secondary Endpoints

- Change from Baseline over time in total number of errors on the GMLT by study treatment and the derived pharmacodynamic (PD) parameters, as follows:
 - GMLT area under the effect curve from time 0 hours to time t ($AUEC_t$) (net area) by study treatment.
 - GMLT maximum observed effect (E_{max}) by study treatment.
 - Time to reach GMLT E_{max} by study treatment.
- Percentage of subjects who have at least 1 treatment-emergent adverse event (TEAE).
- Percentage of subjects who meet the Takeda markedly abnormal value (MAV) criteria at least once postdose for the following:
 - Clinical laboratory parameters.
 - Vital sign measurements.
 - ECG parameters.
- PK parameters of TAK-071 in plasma after a single dose on Day 1, as follows:
 - Maximum observed plasma concentration (C_{max}).
 - Time of first occurrence of C_{max} (t_{max}).
 - Area under the plasma concentration-time curve from time 0 to time t (AUC_t).
 - Area under the plasma concentration-time curve from time t1 to time t2 (AUC_{t1-t2}).
 - Area under the plasma concentration-time curve from time 0 to infinity (AUC_{∞}), as permitted by the data.
 - $t_{1/2z}$ in plasma, as permitted by the data.

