6	A		C		B		E		D
7	B		D		C		A		E
8	C		E		D		B		A
9	D		A		E		C		B
10	E		B		A		D		C

A=scopolamine matching placebo SC + TAK-071 matching placebo PO + donepezil matching placebo PO.

B=scopolamine 0.5 mg SC + TAK-071 matching placebo PO + donepezil matching placebo PO.

C=scopolamine 0.5 mg SC + TAK-071 PO + donepezil matching placebo PO.

[figure not shown]
D=scopolamine 0.5 mg SC + TAK-071 PO + donepezil 10 mg PO.

E=scopolamine 0.5 mg SC + TAK-071 matching placebo PO + donepezil 10 mg PO.

A 3-week (21-day) washout between treatment periods is required because of the long $t_{1/2z}$ of donepezil to minimize the potential for carryover effects.

The planned timing of assessments and meals relative to scopolamine dosing is shown in [Figure 6.d](#).

Figure 6.d PK/PD Assessments and Meal Timing Relative to Scopolamine Administration – Part 2

Note: Solid gray PK/PD symbols indicate predose assessments. Numbers inside symbols indicate scheduled times relative to the respective study drug dosing for the PK analyte. Shaded meal symbols indicate low-calorie, low-fat meals; all other meals are standard.

Scopolamine (0.5 mg) or matching placebo will be administered as a single SC injection.

TAK-071 or matching placebo will be administered as a single PO dose (as DIC) 24 hours before scopolamine administration.

The dose of TAK-071 for Part 2 will be selected depending on the results from Part 1 (initial substudy) and the FIH Study TAK-071-1001; however, under no circumstances will the selected TAK-071 dose exceed the maximum tolerated dose (MTD), or if the MTD is not attained, the highest dose tested in the SRD part of the FIH study.

The precise dosing time of TAK-071 relative to scopolamine will be selected to ensure that both drugs reach their anticipated peak effects at approximately the same time to maximize the potential to observe TAK-071 procognitive effects.

Donepezil (10 mg) tablet (overencapsulated) or matching placebo will be administered as a single capsule PO 3 hours before injecting scopolamine to maximize the chances of observing a reversal of the scopolamine-induced cognitive impairment.

Blood samples for the analysis of TAK-071, scopolamine, and donepezil plasma concentrations will be obtained at specified time-points up to 10 hours after scopolamine dosing.

CCI

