The SC dose of 0.5 mg is a safe and efficacious dose for the purpose of this study's endpoints. This dose has been previously found to result in maximal cognitive impairment with minimal associated sedation and/or fatigue [29]. SC administration will provide the advantage of better reproducibility, or lower variability, in the dynamic changes in the cognitive impairment profile over time. This is important to ensure that most subjects will attain maximal cognitive impairment at approximately the same time (approximately 2 hours postdose).

6.3.4 **Justification for Endpoints**

The CogState GMLT will serve as the primary outcome measure in this study. From a psychometric perspective, the GMLT can be repeated often in an experimental setting and with little or no practice effect. From a construct validity aspect, the GMLT measures a variety of cognitive functions (immediate and short-term memory for visuospatial information), and it is sensitive to the detection of subclinical perseverative errors and slowed information-processing speed.

6.4 **Premature Termination or Suspension of Study or Study Site**

6.4.1 **Criteria for Premature Termination or Suspension of the Study**

The study will be completed as planned unless one or more of the following criteria are satisfied that require temporary suspension or early termination of the study.

- Study discontinuation due to non-safety reasons such as:
 - A finding (eg, PK, PD, efficacy, biologic targets, etc) from another nonclinical or clinical trial using the trial treatment(s) that results in the trial being stopped for a non-safety related reason.
 - Data from comparator(s), drug(s) of the same class, or methodology(ies) used in this trial become available and results in the trial(s) being stopped for a non-safety related reason.
 - The study is stopped due to non-scientific and non-safety reasons, such as slow enrollment.
- Study discontinuation due to safety reasons:
 - Early trial termination due to unanticipated safety concerns arising from clinical or nonclinical trials with the trial treatment(s), comparator(s), drug(s) of the same class or methodology(ies) used in this trial.
 - New information or other evaluation regarding the safety or efficacy of the study drug that indicates a change in the known risk/benefit profile for the product, such that the risk is no longer acceptable for subjects participating in the study.

6.4.2 **Criteria for Premature Termination or Suspension of Study Sites**

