9.1.16 PD Parameters (Only for Part 2)

CCI

The PD parameters will include the following:

Symbol/Term	Definition
AUEC _t	Area under the effect curve from time 0 to time t
E _{max}	Maximum observed effect
Time to E _{max}	Time from scopolamine dosing to occurrence of E _{max}

Additional PD parameters may be estimated and/or reported, as appropriate.

CCI

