13.1.4 PD Analysis

13.1.4.1 Cognitive Testing Analysis

To address the statistical hypotheses related to the time course of scopolamine effects, cognitive endpoints will be analyzed using a mixed analysis of variance (ANOVA) model appropriate for a 5-period crossover with fixed factors for period, sequence, treatment, hour, and treatment by hour. Additionally, the model will contain a random factor subject nested in sequence (the between-subject error) and a random residual error term (the within-subject error). A 2-sided t-test ($\alpha=0.05$) using the within subject mean squared error from the mixed ANOVA model will be examined to test the primary hypothesis. Treatment differences, 2-sided 95% CIs, 2-sided p-values, and effect sizes will be presented for all time points, with 2 hours post scopolamine being the time frame for the primary endpoint.

To address the statistical hypotheses related to area under the effect curve (AUEC) endpoints, cognitive endpoints will be analyzed using an ANOVA model appropriate for a 5-period crossover with fixed factors for treatment, period, and sequence. Additionally, the model will contain a random factor subject nested in sequence (the between-subject error) and a random residual error term (the within-subject error). A 2-sided t test ($\alpha=0.05$) using the within subject mean squared error from the mixed ANOVA model will be examined to test the statistical hypothesis.

For AUEC endpoints, the natural log scale treatment differences (eg, the primary treatment comparison of Treatment Y – Treatment X) will be exponentiated and reported as a mean percent change along with 95% CIs for the true mean percent change as a summary measure. Other statistical treatments (such as multivariate analysis of covariance [ANCOVA]) will be outlined in the SAP.

The Baseline cognitive measure will be included in the model as a covariate.

Other statistical analyses will be performed as appropriate.

13.1.4.2

CCI

CCI

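### GMLT AUEC is a net (signed) area under change from Baseline, but the protocol summarises AUEC on the log scale as a percent change, which is undefined at or below zero

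*Protocol*

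**What the plan says.** **Endpoint.** The parent entry in Protocol 5.2.2 is "Change from Baseline over time in total number of errors on the GMLT by study treatment and the derived pharmacodynamic (PD) parameters". Beneath it stands GMLT AUEC, an entry that ends "net area) by study treatment". The synopsis (2.0) repeats this. The parameter table in 9.1.16 says only "Area under the effect curve from time 0 to time t".

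**Analysis.** 13.1.4.1 puts AUEC into a crossover ANOVA with treatment, period and sequence as fixed effects and subject within sequence as a random effect. It then says: "For AUEC endpoints, the natural log scale treatment differences" (illustrated with a generic pair of treatments) "will be exponentiated and reported as a mean percent change along with 95% CIs for the true mean percent change". Baseline is a covariate. The synopsis carries the same rule.

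**Deferral.** 13.1.4.1 adds "Other statistical treatments (such as multivariate analysis of covariance [ANCOVA]) will be outlined in the SAP", and 13.1 leaves further detail on analysis variables and methods to the SAP. SAP 7.10.3 neither lists nor summarises the PD parameters, because Part 2 stopped early.

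**The no-challenge arm.** Table 6.a defines "A=scopolamine matching placebo SC + TAK-071 matching placebo PO + donepezil matching placebo PO". Section 6.3.4 says "the GMLT can be repeated often in an experimental setting and with little or no practice effect".

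**The concern.** A net area lets time below Baseline cancel time above it. Its no-effect value is zero, and zero or negative results are ordinary outcomes. A log-scale summary needs strictly positive values.

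If the rule were applied as written, values at or below zero would drop out unless someone chose an offset after seeing the data. The loss would not be random. It would fall most heavily on Treatment A, which is one of the five treatments in the model. With impairment coded positive, it would also remove the scopolamine periods in which the deficit was most fully reversed, which are the periods of most interest. Small positive areas would stay in but become large negative logs with undue influence.

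**Working it through.** **1. The plan's own figure.** No figure is given for AUEC. The nearest is the 90% power for the primary GMLT comparison (13.3: 26 completers, effect size 0.67, 2-sided alpha 0.05). A paired t-test with noncentrality 0.67 × √26 and 25 df gives 90.7%, so that figure reproduces. It concerns the 2-hour endpoint and does not depend on AUEC.

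**2. Can the area be zero or negative?** Take illustrative changes from Baseline at 0, 1, 2, 3, 4, 6, 8 and 10 h (assumed profiles, trapezoidal rule):

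| Profile | Changes | Net area (error-hours) | ln |
|---|---|---|---|
| Errors rise, then recover | 0, 15, 20, 14, 8, 3, 0, 0 | 7.5 + 17.5 + 17 + 11 + 11 + 3 + 0 = 67 | 4.20 |
| Flat | all 0 | 0 | undefined |
| Slight drift below Baseline | 0, −1, −2, −1, 0, 1, −1, −2 | −0.5 − 1.5 − 1.5 − 0.5 + 1 + 0 − 3 = −6 | undefined |
| First profile, opposite sign | as row 1, negated | −67 | undefined |

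**3. How often?** The documents give no AUEC mean or SD, so normality and the ratio r = mean/SD are assumptions. The share that cannot be logged is p = Φ(−r). The expected number among 26 completers in one treatment is 26p. The chance of at least one such value is 1 − (1 − p)^26.

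| r | p | 26p | P(at least one of 26) |
|---|---|---|---|
| −0.5 | 69% | 18.0 | practically 1 |
| 0 | 50% | 13.0 | practically 1 |
| 0.5 | 31% | 8.0 | practically 1 |
| 1 | 16% | 4.1 | 99% |
| 1.5 | 7% | 1.7 | 83% |
| 2 | 2% | 0.6 | 45% |
| 3 | 0.1% | 0.04 | 3% |

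**4. Reading the table.** In Treatment A nothing is given that should move the score, and the protocol expects little practice effect, so r near 0 is the natural starting point. At r = 0 the share is 50% whichever direction is coded positive. The rows from −0.5 to 0.5 show the sensitivity to a modest drift. The scopolamine treatments belong in the lower rows if impairment is coded positive. Enrichment for scopolamine responders (7.3) may favour the higher ratios there, but it does nothing for Treatment A.

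**5. The percent change.** With the profiles above, the ratio of the scopolamine area to the drifting placebo area is 67/(−6) = −11.2, which cannot be read as a percent change. With the flat profile as reference it does not exist.

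**The case against.** - **AUEC may mean raw error counts.** Section 9.1.16 does not mention change, and a log summary with a Baseline covariate would suit a non-negative area. This reading is possible but less natural: raw counts cannot go negative, so calling the area net would add nothing, and the entry sits under change from Baseline. If raw counts were meant, 5.2.2 and the synopsis need correcting instead.
- **The detail was for the SAP, or is redacted.** Section 13.1 does defer definitions and methods, and parts of 9.1.15, 9.1.16 and 13.1.4.2 are blacked out. A handling rule may exist there, so its absence is not established. But the two statements in conflict are both readable, and the SAP does not reconcile them because it drops the PD analyses.
- **The test itself may not be on logs.** The sentences that set up the ANOVA and t test mention no transformation; the log sentence concerns the reported summary. A reader might infer that the AUEC hypothesis test cannot be run. The text does not go that far: what fails is the stated summary and its interval.
- **Treatment A is not in the comparison that matters most.** The stated primary comparison is TAK-071 plus scopolamine against placebo plus scopolamine. A reader might take the 50% as a loss across all treatments; it applies to Treatment A alone, under an assumed zero mean. Baseline is taken on Day 1 and the area runs over Day 2, so drift could move that mean.
- **The sign in 7.3.** The enrichment criterion writes impairment as a change of −5 or lower. A reader might infer that nearly all scopolamine areas would be negative. No readable passage says that AUEC uses that sign, so this does not follow.

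**Conclusion.** In the readable text the log and percent-change summary does not fit GMLT AUEC as a net area of change from Baseline. The size depends on assumptions. In Treatment A about half the values are unusable if the distribution is symmetric about zero, and 31% to 69% if it is normal with a mean within half an SD of zero. In the scopolamine treatments the share is about 16% to 0.1% at mean/SD of 1 to 3 with impairment coded positive.

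The point is minor. It concerns one secondary PD endpoint in the protocol as planned. The 2-hour primary analysis and the sample size are unaffected. A reader might infer that trial results were compromised; they were not, because no subject began Period 2 (SAP 7.1) and the SAP reports no PD endpoint.

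**What to change.** For GMLT net AUEC only, in 13.1.4.1 and the synopsis:

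- Exempt it from the log and percent-change sentence.
- Analyse it untransformed in the same crossover ANOVA with Baseline as covariate, and report treatment differences in error-hours with 95% CIs.
- State which direction of change means impairment.

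Alternatively, if a ratio is wanted, correct 5.2.2 and the synopsis so that AUEC is defined on raw error counts, and prespecify a rule for an area of zero.

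Do not delete the log sentence for every cognitive AUEC. It covers the whole battery, and Table 9.d lists tasks in log10 milliseconds and arcsine proportions, for which error-hours would make no sense. Keep the log and percent summary for those only where the area is strictly positive.

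The cost is one sentence in each of two places plus a sentence on direction. No data or sample size is lost and every observed area is kept; the GMLT summary is read in error-hours instead of percent.

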13.1.5 Safety Analysis

The safety of TAK-071 in combination with scopolamine will be assessed through AEs, clinical laboratory results, physical examination findings, ECG findings, vital signs, and suicidal assessments.

Summary tables will include the number and percent of subjects in each treatment experiencing at least 1 TEAE by system organ class and preferred term. If a subject has more than 1 AE that codes to the same preferred term, the subject will be counted only once for that preferred term. Similarly, if a subject has more than 1 AE within a system organ class category, the subject will be counted only once for that system organ class.

TEAEs possibly or probably related to study medication will be tabulated in the same manner. TEAEs will also be summarized by maximum intensity. All AEs will be listed.

AEs will be summarized using the safety analysis set. All AEs will be coded using MedDRA. Data will be summarized using preferred term and primary system organ class.

Clinical laboratory tests (hematology, chemistry, and urinalysis), vital signs, and ECG parameters will be listed. The results that meet TDC markedly abnormal criteria will be flagged in the listing.

The percentage of subjects who meet TDC markedly abnormal criteria at least once postdose will be summarized.

13.2 Interim Analysis and Criteria for Early Termination

No interim analysis is planned.

13.3 Determination of Sample Size

For Part 1, a sample size of 6 enrolled and 4 completers is considered sufficient for providing guidance on the TAK-071 dose selection for Part 2, the main study. This is not based on any statistical power.

For Part 2, a sample size of 26 subjects, approximately 3 subjects for each of the 10 sequences of the 5-period cross-over, will be used and is considered sufficient for evaluation of the primary cognitive endpoints for this study based on consideration of published scopolamine model literature and expert advice. Subjects who drop-out will not be replaced, therefore to ensure there are enough completers a total of 40 subjects will be recruited (4 per sequence).

In particular, this sample-size calculation was based on a consideration of effect sizes seen in a similar study [21]. Using a 2-sided alpha level of 0.05, this study has a 90% power to detect an effect size of 0.67 in the GMLT (sum of 5 trials) total number of errors for the primary treatment comparison of TAK-071+scopolamine vs placebo+scopolamine, assuming a total of 26 subjects complete the study and provide primary endpoint data.

At least 26 subjects will complete the study if 40 subjects are randomized, assuming the drop-out rate does not exceed 33%.

14.0 QUALITY CONTROL AND QUALITY ASSURANCE

14.1 Study-Site Monitoring Visits

Monitoring visits to the study site will be made periodically during the study to ensure that all aspects of the protocol are followed. Source documents will be reviewed for verification of data recorded on the eCRFs. Source documents are defined as original documents, data, and records. The investigator and study site guarantee access to source documents by the sponsor or its designee (contract research organization [CRO]) and by the IRB.

All aspects of the study and its documentation will be subject to review by the sponsor or the sponsor's designee (as long as blinding is not jeopardized), including but not limited to the Investigator's Binder, study drug, subject medical records, informed consent documentation, documentation of subject authorization to use personal health information (if separate from the informed consent forms), and review of eCRFs and associated source documents. It is important that the investigator and other study personnel are available during the monitoring visits and that sufficient time is devoted to the process.

14.2 Protocol Deviations

The investigator should not deviate from the protocol, except where necessary to eliminate an immediate hazard to study subjects. Should other unexpected circumstances arise that will require deviation from protocol-specified procedures, the investigator should consult with the sponsor or designee (and IRB or IEC, as required) to determine the appropriate course of action. There will be no exemptions (a prospectively approved deviation) from the inclusion or exclusion criteria.

The site should document all protocol deviations in the subject's source documents. In the event of a significant deviation, the site should notify the sponsor or its designee (and IRB as required). Significant deviations include, but are not limited to, those that involve fraud or misconduct, increase the health risk to the subject, or confound interpretation of primary study assessment. A Protocol Deviation eCRF should be completed by the site and acknowledged by the sponsor or designee for any significant deviation from the protocol.

Every attempt will be made to collect each PK blood sample at the designated time point, and the actual time of each blood sample will be recorded on the source document and eCRF. [Table 14.a](#) defines the windows allowed for sample collections.

However, blood samples not collected within the interval specified for the scheduled sample time should be documented as deviations in the site source document.

Table 14.a Windows for PK Blood Sample Collection

Minutes	Nominal Sampling Time
no more than 30 minutes predose	0 hour
±5	postdose to <24 hours
±30 minutes	>24 to ≤96 hours
±24 hours	>96 hours

14.3 Quality Assurance Audits and Regulatory Agency Inspections

The study site also may be subject to quality assurance audits by the sponsor or designees. In this circumstance, the sponsor-designated auditor will contact the site in advance to arrange an auditing visit. The auditor may ask to visit the facilities where laboratory samples are collected, where the medication is stored and prepared, and any other facility used during the study. In addition, there is the possibility that this study may be inspected by regulatory agencies, including those of foreign governments (eg, the Food and Drug Administration [FDA], the United Kingdom Medicines and Healthcare products Regulatory Agency, the Pharmaceuticals and Medical Devices Agency of Japan). If the study site is contacted for an inspection by a regulatory body, the sponsor should be notified immediately. The investigator and institution guarantee access for quality assurance auditors to all study documents as described in Section [14.1](#).

15.0 ETHICAL ASPECTS OF THE STUDY

This study will be conducted with the highest respect for the individual participants (ie, subjects) according to the protocol, the ethical principles that have their origin in the Declaration of Helsinki, and the ICH Harmonised Tripartite Guideline for GCP. Each investigator will conduct the study according to applicable local or regional regulatory requirements and align his or her conduct in accordance with the “Responsibilities of the Investigator” that are listed in [Appendix B](#). The principles of Helsinki are addressed through the protocol and through appendices containing requirements for informed consent and investigator responsibilities.

15.1 IRB

IRBs must be constituted according to the applicable state and federal/local requirements of each participating region. The sponsor or designee will require documentation noting all names and titles of members who make up the respective IRB. If any member of the IRB has direct participation in this study, written notification regarding his or her abstinence from voting must also be obtained. Those Americas sites unwilling to provide names and titles of all members due to privacy and conflict of interest concerns should instead provide a Federal Wide Assurance Number or comparable number assigned by the Department of Health and Human Services.

The sponsor or designee will supply relevant documents for submission to the respective IRB for the protocol’s review and approval. This protocol, the Investigator’s Brochure, a copy of the informed consent form, and, if applicable, subject recruitment materials and/or advertisements and other documents required by all applicable laws and regulations, must be submitted to a central or local IRB for approval. The IRB’s written approval of the protocol and subject informed consent must be obtained and submitted to the sponsor or designee before commencement of the study (ie, before shipment of the sponsor-supplied drug or study specific Screening activity). The IRB approval must refer to the study by exact protocol title, number, and version date; identify versions of other documents (eg, informed consent form) reviewed; and state the approval date. The sponsor will ship drug/notify site once the sponsor has confirmed the adequacy of site regulatory documentation and, when applicable, the sponsor has received permission from competent authority to begin the study. Until the site receives drug/notification no protocol activities, including Screening may occur.

Study sites must adhere to all requirements stipulated by their respective IRB. This may include notification to the IRB regarding protocol amendments, updates to the informed consent form, recruitment materials intended for viewing by subjects, local safety reporting requirements, reports, and updates regarding the ongoing review of the study at intervals specified by the respective IRB, and submission of the investigator’s final status report to IRB. All IRB approvals and relevant documentation for these items must be provided to the sponsor or its designee.

Subject incentives should not exert undue influence for participation. Payments to subjects must be approved by the IRB and sponsor.

